Study Design	Open label comparison of two proven interventions in COPD to assess responsiveness of exercise tests
Study Participants	Adult COPD subjects
Planned Sample Size	 Phase 1, n=60 (to allow for drop out & interim analysis after the last visit of patient #50) Phase 2, further 79 (allowing for a 25% drop out) Total recruitment of 139 subjects
Follow-up duration	Six weeks
Planned Study Period	17 Months – Phase 1 (March 2013 – December 2014) 24 Months – Phase 2 (December 2015 – November 2017)
Aims	To assess the responsiveness of a range of exercise tests in relation to six minute walk
Outcome measures	ISWT, ESWT, 6MWT, endurance cycle, incremental cycle, SPPB, PROactive, Accelerometery.

Aim

By conducting a comprehensive comparison of exercise tests commonly employed to assess functional capacity in subjects with COPD we aim to secure a wider understanding of the relative properties (stability and sensitivity) of the these tests to guide clinical trial outcome selection. The study will produce data which are sufficiently robust to provide information for the regulatory bodies regarding the assessment of activity limitation in COPD for future clinical trials.

Hypothesis

The 6MWT is the least sensitive test that can be employed in the assessment to response to treatment of either pulmonary rehabilitation or bronchodilator therapy.

Background

Exercise outcomes are required to capture outcomes relevant to subjects missed by spirometry

Traditional measures of airflow obstruction such as FEV_1 offer an inadequate reflection of the impact of COPD and are not influenced by otherwise effective therapy, particularly pulmonary rehabilitation (1, 2). Conversely exercise tests are used to assess activity limitation (disability) and are capable of improvement after various therapies, including bronchodilators (3). Several exercise tests have been described for this purpose. The existing tests vary in the required physical environment (laboratory vs. field), exercise platform (cycling vs. walking) or protocol (maximal vs. endurance, paced vs. self-paced). There has been no comprehensive comparison of the relative reproducibility and sensitivity of these tests when performed concurrently.

Existing tests span a range of complexity

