Subjects (approximately, to allow for withdrawals) will be recruited from clinics, trial registers and pulmonary rehabilitation (PR) waiting lists along with subjects identified from primary care COPD registers and poster response from displays at GP practices and hospitals. Subjects will be randomised to one of 3 groups (control:PR:LAMA) in a 1:2:2: allocation for phase 1 and a 1:1:4 for phase 2 of the trial. The aim will not be to evaluate the interventions but simply to produce a range of change in performance so that the changes in the exercise tests employed can be evaluated. The five most commonly reported exercise tests, strength testing and the Short Physical Performance Battery will be examined at baseline and after 6 weeks of the intervention or control period. The outcome measures will be conducted by blinded assessors. A planned analysis will be conducted after the 50th patient's last visit to confirm that commitment of the full resource and the 'opening' of other sites will deliver the desired data.

Eligible participants

The subjects will have a confirmed diagnosis of COPD and have GOLD stage 2-4 disease, and MRC grade dyspnoea2 or greater. Participants will be restricted to 40-85 years, so that they align with the 'classic' COPD patient. Since the aim is to compare different exercise outcomes, participants will not be stratified by exercise performance at baseline. However review of two sites (Leicester and RBHT) entrants to pulmonary rehabilitation programs suggests, based on ISWT data, that ~80% of participants will have an 6MWT <350m¹.

Exclusion criteria

Participants will be excluded from the trial if they have co-morbidities that limit the ability to walk/cycle, for example musculo-skeletal, arthritic, or neurological disorders. Common COPD co-morbidities such as controlled hypertension or heart failure will not be excluded, but will be documented. Since rehabilitation

¹ For example of 173 consecutive subjects in a currently submitted MS from Harefield the 75th centile for ISWT was 283m.

is one of the interventions, subjects who have participated in rehabilitation over the last 12 months will also be excluded, simply because they may not then gain additional benefit. Participants using LTOT therapy will also be excluded as will those requiring oxygen therapy during the course of an exercise test (i.e. desaturation documented below 85%)

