Six week bronchodilator therapy (LAMA; Tiotropium). It is likely that a significant number of subjects recruited for this trial will have already been prescribed Tiotropium in line with NICE guidelines, and these subjects, if randomised to this arm, will be required to withdraw from this for a period for a two week washout. Tiotropium will be replaced by the prescription of a short-acting muscarinic antagonist bronchodilator therapy (SAMA) for this two week washout. These subjects will then recommence inhaled Tiotropium following baseline testing at visits two and three.

For subjects recruited but prescribed a LAMA combination inhaler the prescription will be amended to reflect the above washout though replacing any inhaled long-acting beta₂ adrenergic receptor agonists or corticosteroids with the recommended alternative along with the above described SAMA and for the duration of the washout phase. Following this two week period, baseline measures will be conducted as described above. This will afford the opportunity to observe the possible detrimental effect of withdrawing Tiotropium. After reassessment of six weeks of regular bronchodilator therapy with Tiotropium (plus replacement alternatives) all outcome measures will be repeated. If subjects have not previously been prescribed a LAMA they will continue with any current prescribed inhaler therapy and if randomised to LAMA will commence the 'LAMA' arm of the trial after visit 3. Inhaler technique will be assessed and confirmed to be acceptable. Any changes in prescription will be notified to the subjects General Practitioner/Respiratory physician where future care provision will be assessed.

Intervention 2

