For each exercise test conducted in the laboratory an online gas analysis system will be employed. This will not be possible for field based exercise tests. The following baseline variables will be collected for all tests, not necessarily all on every occasion but where appropriate documented at every visit.

- 1. Baseline spirometry (lung volumes and diffusing capacity of the lung for carbon monoxide (DLCO) to be done at entry only)
- 2. Height/weight (BMI)/leg length(ASIS to Medial Malleolus)
- 3. Fat free mass index by bio-electrical impedance⁶
- 4. Resting Heart rate
- 5. Resting fingertip oxygen Saturation
- 6. MRC dyspnoea score
- 7. Resting Borg breathlessness & RPE Scale

At the start and end of each exercise test, as well as all performance measures we will record-

- 1. Saturation
- 2. Heart rate
- 3. Blood pressure
- 4. Borg breathlessness & leg exertion
- 5. Reason for termination
- 6. For the 6MWT we will record the number and time of stops.

At baseline and after 6 weeks the exercise tests will be conducted over 4 visits following a day of familiarisation.

Visit 1 (1 day visit or split over 2 consecutive days) – Familiarisation

Consent and Eligibility confirmation

⁵ So as a secondary aim possibly generating insights into order effects

⁶ Glenfield use Bodystat[®] 1500.

Subjects will be given the opportunity to attend the initial consent and eligibility screening (including spirometry) prior to committing to a whole or half day of testing.

- 1. Informed consent secured
- 2. Spirometry (gas transfer and full lung function test)
- 3. Individuals will be randomised to one of three groups as described in figure 1.
- 4. Baseline questionnaires
- 5. Apply physical activity monitors
- 6. Isometric muscle strength (QMVC)
- 7. Exercise testing will be completed in random order. There will be a minimum of 30 minutes rest between each test, in addition two activity monitors will be given to the individual, to be worn for 14 days (24 hours a day). These will also be worn during exercise testing for visits 1, 2, 3, 4 and 5 to gauge intensity and energy expenditure.
 - Maximal cardiopulmonary cycle test & Endurance cycle test
 - 6 MWT (practice)
 - ISWT (practice) & ESWT (practice)
 - SPPB

Visit 2 (two weeks later, after activity monitor data collection period) - Baseline

Exercise tests will be presented in random order. There will be at least 30 minutes rest between each test.

- a. Maximal incremental cardiopulmonary cycle test

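### Randomisation is step 3 of Visit 1, before the only baseline health questionnaires and before any exercise test that could reveal the desaturation exclusion; it should be the last step of that visit

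*Protocol*

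**What the plan says.** **Order at Visit 1.** The protocol's Testing procedure section gives Visit 1 as a numbered list under a line on consent and eligibility confirmation: consent (1), spirometry and lung function (2), randomisation (3), questionnaires (4), activity monitors (5), quadriceps strength (6), exercise tests (7). Step 3 is "Individuals will be randomised to one of three groups as described in figure 1", the next line is "4. Baseline questionnaires", and the exercise tests appear only at "7. Exercise testing will be completed in random order". Patients may attend beforehand for "initial consent and eligibility screening (including spirometry) prior to committing to a whole or half day of testing"; no exercise test is named as part of that screening.

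**Exclusion.** The Exclusion criteria section rules out "those requiring oxygen therapy during the course of an exercise test (i.e. desaturation documented below 85" per cent.

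**Questionnaires.** The Schedule of Visits places the health questionnaires at Visit 1 and at Visits 4 and 5 only. The sub-study on the MCID relates change in exercise performance to the CRQ.

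**Blinding.** The synopsis describes the trial as "Open label comparison of two proven interventions in COPD to assess responsiveness of exercise tests". The exercise-test assessors are stated to be blinded to allocation and to prior performance.

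**Washout.** Under Method and Intervention 1, LAMA is withdrawn for two weeks before baseline only in patients allocated to LAMA. Patients not previously on a LAMA who are allocated to it begin the LAMA "arm of the trial after visit 3".

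**The concern.** Eligibility should be settled before allocation. Here one criterion depends on what happens during exercise, and the trial's own first look at that comes four steps after randomisation. The protocol does not say what happens to a patient who desaturates after being allocated. Exercise data are analysed per protocol, so such a patient would probably drop out of the analysis and use up part of the attrition allowance.

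The second issue is the questionnaires. They are self-completed, so assessor blinding does not protect them. Their single baseline is collected after allocation in an open-label trial. The planned comparisons are of change within each group, so any influence of knowing the arm on the baseline passes straight into the change score. For the CRQ, that change also feeds the derivation of MCIDs for the exercise tests.

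**Working it through.** **Step 1. What comes before and after allocation under the current list**

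| Item | Where scheduled | Relative to randomisation (Visit 1, step 3) |
|---|---|---|
| Consent, spirometry | Visit 1, steps 1-2 | Before |
| Health questionnaires, only baseline | Visit 1, step 4 | After |
| 14-day activity monitoring | From Visit 1, step 5 | After |
| Strength, first measurement | Visit 1, step 6 | After |
| First exercise tests (first chance to see desaturation) | Visit 1, step 7 | After |
| Baseline incremental cycle, 6MWT, ISWT, strength | Visit 2 | After |
| Baseline ESWT, endurance cycle, SPPB | Visit 3 | After |

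With randomisation moved to the end of Visit 1, the questionnaires, first strength measurement and first exercise tests come before it. The last two rows and the 14-day monitoring period do not.

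**Step 2. The plan's own sample size.** Inputs, from the section on sample size re-estimation: mean ESWT change 60 s, SD 160 s, 80% power, alpha 5%. The one-sample, two-sided t-test is as stated for the protocol's 50 s calculation. With noncentrality 60/160 × √n and n − 1 degrees of freedom, n = 58 gives power 80.2%. With 25% attrition, 58/0.75 = 77.3, rounded up to 78. Both stated figures reproduce. The LAMA attrition allowance is 78 − 58 = 20.

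**Step 3. Who can still be affected.** From Table 5:
- already allocated: 18 + 34 + 42 = 94
- still to randomise: 9 + 0 + 36 = 45
- total: 94 + 45 = 139

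**Step 4. Avoidable exclusions.** The documents give no rate of exercise desaturation, so 5-15% is an assumption.
- all remaining patients: 45 × 0.05 = 2.25 and 45 × 0.15 = 6.75, about 2-7
- remaining LAMA patients: 36 × 0.05 = 1.8 and 36 × 0.15 = 5.4, about 2-5
- share of the allowance: 2/20 = 10% to 5/20 = 25% (9% to 27% before rounding)

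**Step 5. Effect on power if these losses come on top of the planned 25%.** Take the 42 LAMA patients already allocated as losing 25% only:
- at 5%: 42 × 0.75 + 36 × 0.75 × 0.95 = 31.5 + 25.65 = 57.15, so 57 evaluable, power 79.5%
- at 15%: 31.5 + 36 × 0.75 × 0.85 = 31.5 + 22.95 = 54.45, so 54 evaluable, power 77.2%

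If the 25% already covers such exclusions, power stays at 80.2%.

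**The case against.** The strongest case on the other side is that early allocation is deliberate. Prior LAMA users allocated to LAMA must stop two weeks before baseline, so allocation has to come near Visit 1. The aim is to compare tests rather than treatments, the powered analysis is within the LAMA arm, and the assessors are blinded. All of that stands, and it limits the harm. It does not explain why allocation must precede the questionnaires and the first exercise tests on the same visit, since the end of Visit 1 leaves about the same two weeks.

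Several stronger readings are tempting and are not supported:

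- *A reader might infer that ineligible patients are being randomised.* The documents show only that they can be. The criterion speaks of documented desaturation, which earlier records might supply.
- *A reader might infer that Visit 1 exclusions differ by arm because only one arm has a drug withdrawn.* The Visit 1 tests come before any washout, so withdrawal cannot produce that difference. It could at Visits 2 and 3, but the reorder does not touch those.
- *A reader might infer that reordering protects the 6MWT baseline.* The Visit 1 walk is a practice walk; the baseline walks are at Visit 2, after allocation either way.
- *A reader might want the arm withheld until after Visit 3 wherever no washout is needed.* A prior LAMA user who is not told to wash out could then infer that they are not in the LAMA arm, and the protocol expects many prior users.
- *A reader might apply the assumed rate to all 139 patients, or all 78 LAMA patients.* Table 5 shows 94 and 42 of these already allocated, beyond the reach of any change.

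The protocol also does not say when participants learn their arm. Prior LAMA users allocated to LAMA must know before Visit 2; for others, knowledge on the day of Visit 1 is likely in an open-label trial but not stated.

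**Conclusion.** The point holds in a limited form. The written order allows randomisation before the desaturation criterion has been checked, and puts the only questionnaire baseline after allocation. Both are avoidable without disturbing the arm-specific washout.

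The questionnaire part follows from the schedule alone and needs no assumption about rates, although the documents do not allow the size of any bias to be estimated. The exclusion part is small: about 2-7 of the 45 remaining patients, or 2-5 of the 36 for LAMA, using 10-25% of the 20-patient allowance. That rests on an assumed 5-15% desaturation rate and on no prior documentation. The 58 and 78 in the sample size are correct and need no revision on this account.

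**What to change.** Make randomisation the last numbered step of Visit 1, after spirometry, questionnaires, strength testing and the familiarisation exercise tests, once eligibility is confirmed. Where Visit 1 is split over two days, count the protocol's existing two-week interval to Visit 2 from the day of allocation, and reconcile the day numbers in the Schedule of Visits with that. State how a patient found to meet the desaturation exclusion after allocation is handled in the analysis and in the counts. Acknowledge that the Visit 2 and 3 exercise baselines and the 14-day activity baseline follow allocation because the washout depends on the arm.

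The cost is a protocol amendment that reorders one list and adds a few sentences. It needs no extra visit, test or staff. The price is that the arm is known a few hours, or one day, later. The change helps only the patients not yet randomised.

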- b. 6 MWT (performed twice with a 30 min rest in-between)
- c. ISWT (performed twice with a 30 min rest in-between)
- d. Strength testing (QMVC)

Visit 3 (next day)

Three exercise tests will be conducted in random order. There will be at least 30 minutes rest between each test.

- e. ESWT (85% peak performance)
- f. Cycle endurance test (85% peak performance)
- g. SPPB

Retesting after completion of the 6 week intervention (visits 4 and 5), will comprise the following measures presented in the same order as baseline (visits 2 and 3). These tests will be completed by a blinded assessor, blind to the intervention and previous results. Two activity monitors will be given, to be worn during visits 4 & 5 and for a further 7 days (24 hours a day).

- 1. ISWT
- 2. 6MWT
- 3. ESWT, at same level as baseline
- 4. Maximal incremental cycle test
- 5. Endurance cycle test, at same workload level and RPM as baseline
- 6. SPPB
- 7. Strength testing (QMVC)
- 8. Health Questionnaires

At the completion of the interventions a global rating scale of change will be reported for each exercise test. This will allow the description of the MID using anchor and distribution based methods. The global rating scale will identify two levels of change (a little improvement and a greater level of improvement). The scale employed will be one recently described by Pepin et al (37) describing the MCID for the ESWT.

Power calculation

In order to calculate a sample size a literature search was conducted using the search terms Tiotropium and six minute walk (and variants e.g. 6MWT) to identify studies giving an estimate of the likely benefit of the drug. Results found are shown in Table 1.

n	Blinded Assessor	Baseline 6MWT (mean (SD))	Tiotropium 6MWT (mean (SD))	Reference	notes
30	n	344 (105)	363 (98)	Fernandes 2010 (38)	Additional use of LABA
38	У	490 (67)	+6 (19)	Oga 2000 (12)	Additional use of Oxitropium
41	n	403 (20)	429 (17)	Fujimoto (39)	-
38	n	222 (5)	+13.5 (2)	Um(40)	-
44	У	415 (75)	429 (70)	Okudan(21)	Single dose (after 120 minutes)

Table 1: Properties of trials investigating Tiotropium with the 6MWT.

Based on these data [name] (Statistician to the Royal Brompton hospital Biomedical Research Unit) estimated the following sample sizes for achieving an increase in 25m in 6MW with 80% power and p=0.05.

Reference	Tio 6MWT (SD of Change From BL)	Estimated Sample size
Fernandes 2010	100 *	128
Oga 2000	19	7
Fujimoto	20 *	7
Um 2007	2	1
Okudan 2006	75 *	73

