For this study we considered, first, that it was important not to have a falsely low sample size and second that most of our subjects would be receiving a LABA. We therefore selected the figure generated by Fernandes paper, of 128 subjects per group but reduced the size of the whole group by 2:2:1 allocation giving a total sample size of 320. The calculation has been reviewed by statisticians from both GSK and Novartis who suggested an interim analysis because of the large range of potential values obtained.

Data entry will be managed by the Leicestershire CTU and held on a secure database. At a pre-agreed time the data will be released to the investigating team, this will be upon completion of the initial baseline measures to explore the stability of the measures and final data release upon completion of the intervention arms of the study. There will is a planned interim data analysis during the intervention phase, after the LV of patient #50. The analysis plan will be pre-defined as described below. There will be a pre-planned sub group analysis on participants with a baseline 6MWT test performance of less than 350m.

Pilot study.

Over the first twelve months a pilot (feasibility) study will be conducted at a single centre (Leicester). Sixty subjects will be recruited allowing for a drop out of 10 and analysis of 50 subjects completing the intervention period & attending all visits; subjects will be randomised and followed up after randomisation to either intervention. The procedure will be as outlined above.

The analysis of this pilot data will be supported by statisticians from Novartis. Preliminary data will be used to confirm the initial power calculations.

For the pilot study web based randomisation, data entry and monitoring will be managed by the Leicester Clinical Trials Unit. The database will be developed to support the multi-centre trial.

Sample Size re-estimation following Pilot Study & Interim Analysis

Upon collection and analysis of interim data, the ESWT was chosen as the exercise measure to recalculate sample size requirements for phase 2. This measure showed high repeatability at initial visits and sensitivity to change within treatment relative to a suggested MCID of 45-85 seconds*. Interim results for ESWT reported a change from baseline of 59 seconds (SD=163 seconds) for the LAMA arm.

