
Based on the interim results, approximately 90 evaluable subjects in the LAMA arm are required to provide >80% power to detect a 50sec change from baseline, assuming a standard deviation of 160sec and a one-sample, two-sided t-test at a significance level of 0.05. To account for a potential 25% dropout rate in Phase 2, 120 subjects will be randomized to the LAMA treatment arm.

The table below shows the number of evaluable subjects needed from the LAMA arm in Phase II to detect a 50 second change from baseline at either 80% or 90% power, given different estimates of standard deviation.

Table of one sample t test power to acted sosse change from baseline					
N needed	SD = 130	SD = 140	SD = 150	SD = 160	SD = 170
Power =80%	56	64	73	83	93
Power =90%	73	85	97	110	124

 Table 3. One-sample t-test power to detect 50sec change from baseline

As changes from baseline are not expected in a control arm, and pulmonary rehabilitation has demonstrated effects in all exercise measures in the interim analysis, these arms will serve mainly to provide additional study sensitivity data. Thus, the randomization allocation will change from 2:2:1 to 4:1:1 to make sufficient within-group comparisons. 30 subjects will be randomized to receive pulmonary rehabilitation and 30 subjects will be randomized as controls in order to provide 22 additional evaluable subjects, plus 8 more to account for a potential 25% dropout rate, in each arm. In total, 180 subjects will be randomized to Phase 2.

2. Sample size re-estimation

WP4 Exercise outcome study

The revised power calculation is aligned with the actual data from the interim analysis. This new calculation is based on a mean change in the ESWT of 60±160 seconds (as per interim analysis) with 80% power and alpha of 5%. A total of 58 subjects are required in the LAMA group and allowing for 25% attrition, a total of 78 recruited subjects are required in the LAMA (table 4). As stated above there is no specific target allocation for placebo or PR in phase 2. We propose to maintain the control arm to provide a negative control to the LAMA arm and reduce the study bias, and allow us to maintain blinding.

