Table 4: One-sample t-test power to detect 60sec change from ba	seline
---	--------

N needed	SD = 130	SD = 140	SD = 160
Power =80%	39	45	58

Randomisation allocation recruitment at Glenfield hospital, Leicester, can be seen in Table 5 (April 2015 – September 2016).

Allocation and Ratio	Control	PR	LAMA
1.2.2 (actual)	16	32	32
1.1.4 (actual)	2	2	10
Current allocated totals	18	34	42
Number required for LAMA (ESWT response of 60±160 sec with 80% power and alpha of 5	-	-	78 recruited 58 completed
New allocation for recruiting n=78 in LAMA (1:0:4)	9	0	36
Total recruited to trial	27	34	78

Table 5: Randomisation allocation over	er time
--	---------

To ensure rigor is maintained a randomisation allocation of 1:0:4 would recruit a further 9 subjects to the control group and a further 36 into the LAMA group.

Analysis Plan

All exercise test data will be analysed on a per protocol basis. All data will be assessed for normality and analysed using appropriate parametric or non-parametric statistics. Significance will be set at p<0.05 and differences will be expressed as mean and standard deviations (SD) or 95% confidence intervals.

Data will be presented as mean (SD) or median (IQR). Comparison of values obtained within the treatment(s) and the control groups will be made using a paired t test or the Wilcoxon signed rank test. All tests will be 2 tailed. Additional analysis will be done to determine the sensitivity and specificity of the other measures to detect the change in MCID. Similarly the sensitivity and specificity of the failure to detect change in the placebo will also be determined.

Reproducibility study – The baseline data will examine the test-re test reproducibility of each of the tests employed, including measures of strength. The primary variable for each test will be the conventional measure of performance. Data will be compared in two ways, firstly the intra-class correlation (ICC) will be reported and secondly limits of agreement using Bland & Altman techniques (41). The Bland & Altman plot will allow us to check the data for stability across a range of performance.

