Sensitivity study - Comparison between the exercise test outcome measures will be made at two separate time points, baseline and 6 weeks. The primary measure for each test will be the variable that is most commonly reported e.g. distance /time/peak oxygen consumption. We will assume that an MCID of 25m is meaningful for 6MWT (15), and assess the ability of other tests to predict this change. Attention will be paid to both floor and ceiling effects.

Data accumulated from individuals offered rehabilitation upon completion of either the control or LAMA arm will be analysed after the main trial has been completed. This data will allow a repeat measures analysis comparing the relative effect of two interventions upon the exercise tests. This is a secondary planned analysis.

Opportunities for sub studies

a) MCID - This study would afford the opportunity to test this assumption and identify an MCID for the exercise tests employed in this study. We will report the MCID in one of two ways, we will employ an anchor based approach and report a statistically general distribution based approach. In addition by relating observed changes in exercise performance to the CRQ we will aim to generate a further MCID for the exercise tests, since it has recently been suggested that an MCID may differ depending on the context and nature of the intervention (37).

Practical Considerations & timescale to do (plus Gant chart)

Three sites should be adequate to recruit the required number of subjects. We estimate that it would take 36 months to complete this study, the pilot study will be conducted over the first year with a recruitment target of n=50. After this pilot phase recruitment will be extended to 3 sites.

Pilot study

Allow 3 months to gain necessary recruitment approval, advertise and recruit staff. To confirm whether MHRA approval required. Completion of ethics submission.

Months 1-3	Finalise ethics approval/set up database & randomisation system with Leicester & staff training as required.	
Month 3-24	Recruit 50 subjects to study – completion of baseline measures	
Month 24-30	Completion of data collection and preliminary analysis	
Month 24-30	Change ethics for multi-centre study	
Month 30-33	Recruitment in place for other sites (2/3)	

Study extension (planned recruitment – 180 participants – 90 per site). Recruitment will continue seamlessly at the Leicester site but allow for 21 months recruitment from the end of the pilot data).

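### The protocol still states 80% power for a 25 m 6MWT change at 128 per group, does not restate it for the 58 LAMA completers now planned, and plans no analysis that directly tests whether the 6MWT is less responsive than the other tests

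*Protocol*

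**What the plan says.** The Hypothesis section states: "The 6MWT is the least sensitive test that can be employed in the assessment to response to treatment", for either rehabilitation or bronchodilator therapy.

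The Power calculation section takes several published tiotropium studies and, from each, "estimated the following sample sizes for achieving an increase in 25m in 6MW with 80% power and p=0.05". The SD column is labelled "Tio 6MWT (SD of Change From BL"). The row adopted has an asterisked SD of 100 m and N = 128. It was chosen to avoid a sample size that was too small. The section then speaks "of 128 subjects per group but reduced the size of the whole group by 2:2:1 allocation giving a total sample size of 320".

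The two re-estimation sections that follow the interim analysis change the basis to the ESWT. The final calculation uses a mean change of 60 s and SD of 160 s, and concludes: "A total of 58 subjects are required in the LAMA group and allowing for 25% attrition", 78 are to be recruited. Table 5 counts those 78 over the whole trial. Neither section gives the interim SD of 6MWT change or the 6MWT power at the new size.

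Under Analysis Plan, within-group change "will be made using a paired t test or the Wilcoxon signed rank test", with p<0.05 as the threshold and the statement "All tests will be 2 tailed". Under Sensitivity study: "We will assume that an MCID of 25m is meaningful for 6MWT (15), and assess the ability of other tests to predict this change".

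**The concern.** The only power statement for the test named in the hypothesis belongs to a sample size the trial no longer plans. A reader of the Power calculation would think a 25 m 6MWT response has an 80% chance of being detected. At the current LAMA target that is true only if the SD of change is well below the value the protocol adopted.

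The second part concerns the analysis. The hypothesis compares tests with one another. The analyses written down examine each test separately within an arm, or use a 25 m 6MWT change as the reference that other tests should predict. Neither estimates how much more or less responsive the 6MWT is than another test. If the ESWT reaches p<0.05 in the LAMA arm and the 6MWT does not, that pattern could be reported as support for the hypothesis without any estimate of the difference. The protocol intends the results for regulators and for choosing outcomes in future trials, so that reading would matter.

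**Working it through.** **Inputs.** 6MWT: change 25 m, SD of change 100 m, 80% power, alpha 0.05 (Power calculation). Two-sided, paired within arm (Analysis Plan). LAMA completers: 58 (re-estimation, Tables 4 and 5). ESWT: 60 s, SD 160 s (same place).

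**Method.** One-sample two-sided t-test on the changes, with exact power from the noncentral t distribution. The normal approximation, power ≈ Φ(√n × change/SD − 1.96), allows a check by hand.

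**Step 1: reproduce the plan.** At n = 128, √128 × 25/100 = 2.83, and Φ(2.83 − 1.96) = 0.81; exact 80.2%. The smallest n with 80% exact power is 128, as stated. The method also returns 73 for SD 75, 7 for SD 19, every cell of Table 3, and 39/45/58 in Table 4. It gives 8, not 7, for SD 20, which has no consequence here. Attrition agrees: 58/0.75 = 77.3, rounded up to 78. A two-sample formula would give 252 per arm, so 128 is a within-group figure.

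**Step 2: the same 6MWT calculation at n = 58.** √58 = 7.616. The last column is the half-width of the 95% confidence interval for mean change, 2.00 × SD/√58.

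| SD of change (m) | 25/SD | Exact power | CI half-width (m) |
|---|---|---|---|
| 100 (adopted row) | 0.25 | 46.5% | 26.3 |
| 75 (another row of the same table) | 0.33 | 70.4% | 19.7 |
| 67 | 0.37 | 79.8% | 17.6 |
| 50 | 0.50 | 96.3% | 13.1 |

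Hand check at SD 100: 7.616 × 0.25 = 1.90, and Φ(1.90 − 1.96) = 0.48. At SD 100, 58 completers have 80% power only for a change of about 37.5 m. At the SDs of 19 and 20 in the same table, power exceeds 99%.

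**Step 3: how firm is SD 100?** In Table 1 the selected study has group SDs of 105 and 98. The SD of change is √(105² + 98² − 2r × 105 × 98), where r is the within-patient correlation. The protocol does not give r, so this is an assumed range: r = 0.5 gives 101.7, r = 0.7 gives 78.9, r = 0.8 gives 64.5 and r = 0.9 gives 45.9. An SD of change near 100 needs r of only about 0.5.

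**Step 4: the ESWT at n = 58.** 60/160 = 0.375; exact power 80.2%. Both tests have the same n, so 47% against 80% reflects only the ratios 0.25 and 0.375.

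**Step 5: do separate tests answer the hypothesis?** Suppose both tests truly had a standardised response mean of 0.375, so about 80% power each. If their results were independent, the chance of a significant ESWT with a non-significant 6MWT would be 0.80 × 0.20 = 0.16, with no difference between the tests. Positive correlation lowers this but does not remove it.

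Now take the inputs at face value: the true difference is 0.375 − 0.25 = 0.125. To leading order, the 95% half-width for a within-patient difference in standardised response mean is 1.96 × √(2(1 − ρ)/58), where ρ is the correlation between the two changes (not in the protocol; assumed). It is 0.36 at ρ = 0, 0.26 at ρ = 0.5 and 0.16 at ρ = 0.8. All exceed 0.125. A split between significant and non-significant results would therefore suggest more certainty than the data hold.

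**The case against.** A reader might infer that sizing the trial on the ESWT biases the comparison against the 6MWT. The documents do not support that. All tests are done by the same patients at the same n, so power differs only through mean change over SD. On the protocol's own inputs the 6MWT would be the less responsive of the two, and a weaker 6MWT result would point the right way.

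A reader might also infer that the protocol will treat a non-significant 6MWT result as proof of insensitivity. It states no such rule. It also plans means with SDs or confidence intervals, sensitivity and specificity against the MCID, and anchor- and distribution-based estimates, and the method of ranking tests may be set out in an SAP that is not shown. This stands as a limit: the point warns about interpretation and about what the stated analyses can answer.

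The change of basis is also open. The protocol explains the wide range of initial sample sizes, says the interim data led to the ESWT, and reports the new total of 139. It nowhere claims 80% 6MWT power at 58, and 58 is correct for the ESWT. Nor should the point extend to the rehabilitation arm, which has no target in phase 2 and which the protocol says showed effects on all exercise measures at the interim.

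Finally, 47% depends on an SD that looks cross-sectional. That is accepted: it is the pessimistic end of the range tabulated above.

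What the objection leaves untouched is that the 6MWT figures were never updated, although the protocol said pilot data would be used to confirm the initial power calculation, and that the comparison between tests is not estimated directly by the analyses stated.

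**Conclusion.** The point holds in limited form. The stated 6MWT sample size and power (128 per group, 320 in total, 80%) do not describe the trial now planned. With 58 LAMA completers, power for 25 m is 46.5% on the protocol's adopted SD, and reaches 80% only if the SD of change is about 67 m or less. The true figure cannot be fixed from the protocol, because the interim SD of 6MWT change is not reported.

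This is a failure to restate a figure, not an arithmetic error. The separate and more consequential gap is that within-arm significance tests, and prediction of a 25 m 6MWT change, do not test relative responsiveness.

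The power figures assume a two-sided one-sample t-test at 0.05 and exactly 58 completers. The illustrations of the difference between tests use assumed correlations.

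**What to change.** 1. In the re-estimation section, state that 128 per group, 320 in total and the 80% 6MWT power no longer apply. Give the 6MWT power, or the expected confidence-interval width, at 58 LAMA completers from the interim SD of 6MWT change. If that SD is not available, give the range: about 47% at SD 100, 70% at SD 75, 80% at about SD 67, 96% at SD 50.

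2. In the Analysis Plan, state that the hypothesis will be judged on the within-patient difference in standardised response mean between the 6MWT and each other test in the LAMA arm, with 95% confidence intervals (for example by bootstrap over patients), and not on which paired tests reach p<0.05.

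The cost is wording, one recalculation from interim data and a small extra analysis. No extra patients are needed. The downsides are a less favourable stated 6MWT power and, as the working suggests, intervals that may be too wide to separate tests with similar responsiveness.
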